Johnson & Johnson Vision Care, Inc.

SYNOPSIS

Protocol Title	Evaluation of Visual Acuity with a Reusable Toric Multifocal Contact Lens
Sponsor	JJVC, [name]
Clinical Phase	Clinical trial phase: Post-market Design control phase: Not applicable.
Trial Registration	This study will be registered on ClinicalTrials.gov based on the following: The clinical trial is evaluating a U.S. FDA-regulated Device Product
Test Article	Marketed Product: Bausch + Lomb Ultra® Multifocal for Astigmatism contact lens manufactured in samfilcon A material.
Wear and Replacement Schedules	Wear Schedule: The lenses will be used on a daily reusable basis for approximately five weeks (1 week trial followed by 4 week dispense of optimized pair). Replacement Schedule: The lenses will be replaced at the first follow-up visit only.
Objectives	Primary Objective The primary objective of this study is an evaluation of the logMAR visual performance with the study lenses after 4 weeks of wear. Secondary Objective Not applicable. Exploratory Objective Not applicable.
Study Endpoints	Primary endpoints: logMAR visual acuity at distance (4 M), intermediate (64 cm) and near (40 cm).
Study Design	The study is a bilateral, single-masked, single-arm, 4-visit dispensing study. There will be one study treatment, with the subject being in the treatment for approximately five weeks. Approximately 90 eligible subjects will be enrolled, with the aim to complete at least 80 subjects. The subjects will be fit in the study lens and wear the study lenses for 5-9 days then undergo optimization and wear the optimized pair for 4 weeks (25-31 days), with an interim follow-up visit at 2 weeks (12-16 days). The primary endpoint will be logMAR visual performance. See the flow chart at the end of the synopsis table for the schematic of the study visits and procedures of main observations (Figure 1).

Clinical Study Protocol
Johnson & Johnson Vision Care, Inc.

Sample Size	Approximately 50 myopic subjects with against-the-rule astigmatism will be enrolled, with the aim that at least 45 will complete the study. Approximately 40 hyperopic subjects with against-the-rule astigmatism will be enrolled, with the aim that at least 35 will complete the study.
Study Duration	The study will last approximately 2-3 months.
Anticipated Study Population	Healthy male and female volunteers with presbyopia, astigmatism and either myopia or hyperopia will be screened as per criteria outlined below. All volunteers will have baseline measurements taken to ensure eligibility. The baseline procedures will occur after informed consent has been obtained. For a detailed list of procedures see the time and events schedule listed below.
Eligibility Criteria	
Potential subjects must satisfy all of the following criteria to be enrolled in the study:
 
Inclusion Criteria following Screening The subject must:
 
 1. Read, understand, and sign the STATEMENT OF INFORMED CONSENT and receive a fully executed copy of the form. 2. Appear able and willing to adhere to the instructions set forth in this clinical protocol. 3. Be at least 40 and not more than 70 years of age at the time of screening. 4. Own a wearable pair of spectacles if required for their distance vision. 5. Be an adapted soft contact lens wearer in both eyes (i.e. has worn lenses a minimum of 2 days per week for at least 8 hours per wear day, for the past month). 6. Be an existing wearer of a presbyopic contact lens correction (e.g., reading spectacles over contact lenses, multifocal or monovision contact lenses, etc.) or respond positively to at least one symptom on the “Presbyopic Symptoms Questionnaire”. 
Inclusion Criteria at Baseline The subject must:
 
 7. Have distance spherical component of refraction in the range of either -1.25 D to -3.75 D or +1.25 to +3.75 D in each eye.

Clinical Study Protocol

Johnson & Johnson Vision Care, Inc.

	
8. Have refractive cylinder in the range of -0.75 D to -1.75 D in each eye, with their cylinder axis $90^\circ \pm 25^\circ$.9. Have near ADD power requirement in the range of +0.75 D to +2.50 D in each eye.10. Have best corrected distance visual acuity of 20/20⁻³ or better in each eye. 
Potential subjects who meet any of the following criteria will be excluded from participating in the study:
 
Exclusion Criteria following Screening The subject must not:
 
1. Be currently pregnant or lactating.2. Have any active or ongoing ocular or systemic allergies that may interfere with contact lens wear.3. Have any active or ongoing systemic disease, autoimmune disease, or use of medication, which may interfere with contact lens wear. This may include, but not be limited to, diabetes, hyperthyroidism, Sjögren's syndrome, xerophthalmia, acne rosacea, Stevens-Johnson syndrome, and immunosuppressive diseases or any infectious diseases (e.g. hepatitis, tuberculosis).4. Use systemic medications that may interfere with contact lens wear or cause blurred vision. See section 9.1 for additional details regarding excluded systemic medications.5. Currently use ocular medication with the exception of rewetting drops.6. Have any known hypersensitivity or allergic reaction to single use preservative free rewetting drops, sodium fluorescein, or Biotrue® multipurpose solution.7. Have any previous, or planned, ocular or intraocular surgery (e.g. radial keratotomy, PRK, LASIK, lid procedures, cataract surgery, retinal surgery, etc.).8. Have a history of amblyopia or strabismus.9. Have a history of herpetic keratitis.10. Have a history of irregular cornea.11. Have a history of pathological dry eye.12. Have participated in any contact lens or lens care product clinical trial within 14 days prior to study enrollment.13. Be an employee or immediate family member of an employee of clinical site (e.g., Investigator, Coordinator, Technician). 
Exclusion Criteria at Baseline

--	--

[figure not shown]
Clinical Study Protocol
Johnson & Johnson Vision Care, Inc.

	
The subject must not:
 
14. Have clinically significant (Grade 2 or greater) corneal edema, corneal vascularization, corneal staining, tarsal abnormalities or bulbar injection, or any other corneal or ocular abnormalities which would contraindicate contact lens wear.
 
15. Have entropion, ectropion, chalazia, recurrent styes, glaucoma, history of recurrent corneal erosions.
 
16. Have any current ocular infection or inflammation.
 
17. Have any current ocular abnormality that may interfere with contact lens wear

Disallowed Medications/Interventions	
Use of any prescription or over-the-counter (OTC) medications that may affect contact lens wear.
 
See section 9.1 for details regarding disallowed systemic medications.

Measurements and Procedures	
The key measurements are logMAR visual acuity at distance (4 M), intermediate (64 cm) and near (40 cm) with the study lenses. See Section 7.2 for the detailed procedures.

Microbiology or Other Laboratory Testing	
None

Study Termination	
The occurrence of one or more Unanticipated Adverse Device Effect (UADE), or any SAE where relationship to study agent cannot be ruled out, may result in stopping further dispensing investigational product. In the event of a UADE or SAE, the Sponsor Medical Monitor may unmask the treatment regimen of subject(s) and may discuss this with the Principal Investigator before any further subjects are enrolled.

Ancillary Supplies/ Study-Specific Materials	
Rewetting drops for optional use during lens wear. Biotrue multi-purpose solution for lens care during dispensing period and for worn lens storage. Lens cases will be provided for temporary contact lens storage during study visits and for use during dispensing periods. Stopwatches will be provided to the site for use during visits.

Principal Investigator(s) and Study Institution(s)/Site(s)	
A full list of Principal Investigators, clinical sites, and institutions is kept separately from the Study Protocol and is included in the study Trial Master File.

Clinical Study Protocol

Johnson & Johnson Vision Care, Inc.

Figure 1: Study Flowchart

Clinical Study Protocol

Johnson & Johnson Vision Care, Inc.

COMMONLY USED ABBREVIATIONS, ACRONYMS AND DEFINITIONS OF TERMS

ADD	Plus Power Required For Near Use
ADE	Adverse Device Effect
AE	Adverse Event/Adverse Experience
BCVA	Best Corrected Visual Acuity
BSCVA	Best Spectacle Corrected Visual Acuity
CFR	Code of Federal Regulations
CLUE	Contact Lens User Experience
COAS	Complete Ophthalmic Analysis System
COM	Clinical Operations Manager
CRA	Clinical Research Associate
CRF	Case Report Form
CRO	Contract Research Organization
CT	Center Thickness
████████	████████
D	Diopter
DMC	Data Monitoring Committee
eCRF	Electronic Case Report Form
EDC	Electronic Data Capture
ETDRS	Early Treatment Diabetic Retinopathy Study
FDA	Food and Drug Administration
GCP	Good Clinical Practice
HIPAA	Health Insurance Portability and Accountability Act
IB	Investigator's Brochure
ICF	Informed Consent Form
ICH	International Conference on Harmonization
IDE	Investigational Device Exemption
IEC	Independent Ethics Committee
IRB	Institutional Review Board
ISO	International Organization for Standardization
ITT	Intent-to-Treat
JJVC	Johnson & Johnson Vision Care, Inc.
LC	Limbus Center
LogMAR	Logarithm of Minimal Angle of Resolution
MedDRA [®]	Medical Dictionary for Regulatory Activities
MOP	Manual of Procedures
NIH	National Institutes of Health
OD	Right Eye
OHRP	Office for Human Research Protections
OHSR	Office for Human Subjects Research
OS	Left Eye
OU	Both Eyes
PD	Protocol Deviation
PHI	Protected Health Information

Clinical Study Protocol

Johnson & Johnson Vision Care, Inc.

PI	Principal Investigator
PIG	Patient Instruction Guide
PQC	Product Quality Complaint
PRO	Patient Reported Outcome
QA	Quality Assurance
QC	Quality Control
SAE	Serious Adverse Event/Serious Adverse Experience
SAP	Statistical Analysis Plan
SAS	Statistical Analysis System
SD	Standard Deviation
SOP	Standard Operating Procedure
UADE	Unanticipated Adverse Device Effect
USADE	Unanticipated Serious Adverse Device Effect
VA	Visual Acuity

Clinical Study Protocol

Johnson & Johnson Vision Care, Inc.

1. INTRODUCTION AND BACKGROUND

Johnson & Johnson Vision launched 1-DAY ACUVUE® MOIST Multifocal in 2015 and ACUVUE® OASYS MULTIFOCAL in 2021. These lenses are recommended for presbyopes who have up to -0.75 D of refractive cylinder. There is a considerable population of presbyopic patients who have greater than -0.75 D of cylinder, in one or both eyes. Currently there are a limited number of soft toric multifocal lenses available. This study will evaluate the visual acuity achieved with one of these marketed lens types (Bausch + Lomb Ultra® Multifocal for Astigmatism).

1.1. Name and Descriptions of Investigational Products

Test Article: Bausch + Lomb Ultra® Multifocal for Astigmatism manufactured in samfilcon A material.

Refer to Table 1: Test Articles in Section 6.1 of the protocol.

1.2. Intended Use of Investigational Products

According to the package insert, the Bausch + Lomb ULTRA® (samfilcon A) Multifocal for Astigmatism Contact Lens is indicated for daily wear for the correction of refractive ametropia (myopia, hyperopia and astigmatism) and presbyopia in aphakic and/or not-aphakic persons with non-diseased eyes, exhibiting astigmatism of up to 5.00 diopters (D) and require an add power ranging from +0.75 D to +5.00 D. In this study, a limited range of refractive corrections (spheres, cylinders and axes) will be evaluated (see section 3.2).

1.3. Summary of Findings from Nonclinical Studies

Not applicable for studies of marketed contact lenses.

1.4. Summary of Known Risks and Benefits to Human Subjects

Not applicable for studies of marketed contact lenses.

1.5. Relevant Literature References and Prior Clinical Data Relevant to Proposed Clinical Study

Information about the Bausch + Lomb Ultra® Multifocal for Astigmatism may be found in the package insert (APPENDIX C: PACKAGE INSERT (APPROVED PRODUCT)).

2. STUDY OBJECTIVES, ENDPOINTS AND HYPOTHESES

2.1. Objectives

Primary Objective

The primary objective of this study is to assess the clinical performance of the study lenses with respect to visual acuity (logMAR) after 4-weeks of lens wear.

Secondary Objective

Not applicable.

Clinical Study Protocol

Johnson & Johnson Vision Care, Inc.

2.2. Endpoints

Primary Endpoint

Visual Acuity (logMAR)

Multiple assessments of binocular and monocular visual acuity will be made during the study, but the binocular measurements made at the 4-week follow-up evaluation using high contrast letters in bright illuminance conditions will be the primary endpoint. At distance (4 meters), VA is assessed using ETDRS Charts; while near (40 cm) and intermediate (64 cm) assessments will be made using reduced Guillon-Poling charts. Visual acuity will be measured using high and low contrast charts in bright illuminance conditions. Visual acuity will also be measured using high contrast charts in dim illuminance conditions created by the use of goggles. See [REDACTED] in Appendix G for details regarding the collection of visual acuity (logMAR).

Secondary Endpoint

Not applicable.

Other Exploratory Endpoint

Not applicable.

2.3. Hypotheses

Primary Hypotheses

1. After 25-31 days of wear, the binocular, high-luminance, high-contrast distance (4 M) logMAR visual acuity of the test lens will be statistically better than 0.00 logMAR. This will be determined using ETDRS LogMAR acuity testing charts.
2. After 25-31 days of wear, the binocular, high-luminance, high-contrast intermediate (64 cm) logMAR visual acuity of the test lens will be statistically better than +0.17 logMAR. This will be determined using Guillon/Poling LogMAR acuity testing charts.
3. After 25-31 days of wear, the binocular, high-luminance, high-contrast near (40 cm) logMAR visual acuity of the test lens will be statistically better than +0.17 logMAR. This will be determined using Guillon/Poling LogMAR acuity testing charts.

3. TARGETED STUDY POPULATION

3.1. General Characteristics

The population to be studied will consist of adapted contact lens wearers who have astigmatism in both eyes. Approximately 90 eligible subjects (50 myopes with against-the-rule astigmatism and 40 hyperopes with against-the-rule astigmatism) will be enrolled with at least 80 targeted to complete. Subjects to be enrolled will have -0.75 D to -1.75 D of astigmatism in both eyes with $90^\circ \pm 25^\circ$ axis.

Clinical Study Protocol

Johnson & Johnson Vision Care, Inc.

3.2. Inclusion Criteria

Potential subjects must satisfy all of the following criteria to be enrolled in the study:

Inclusion Criteria following Screening

The subject must:

1. Read, understand, and sign the STATEMENT OF INFORMED CONSENT and receive a fully executed copy of the form.
2. Appear able and willing to adhere to the instructions set forth in this clinical protocol.
3. Be at least 40 and not more than 70 years of age at the time of screening.
4. Own a wearable pair of spectacles if required for their distance vision.
5. Be an adapted soft contact lens wearer in both eyes (i.e. has worn lenses a minimum of 2 days per week for at least 8 hours per wear day, for the past month).
6. Be an existing wearer of a presbyopic contact lens correction (e.g., reading spectacles over contact lenses, multifocal or monovision contact lenses, etc.) or respond positively to at least one symptom on the “Presbyopic Symptoms Questionnaire”.

Inclusion Criteria at Baseline

The subject must:

7. Have distance spherical component of refraction in the range of either -1.25 D to -3.75 D or +1.25 to +3.75 D in each eye.
8. Have refractive cylinder in the range of -0.75 D to -1.75 D in each eye, with their cylinder axis $90^\circ \pm 25^\circ$.
9. Have near ADD power requirement in the range of +0.75 D to +2.50 D in each eye.
10. Have best corrected distance visual acuity of 20/20⁻³ or better in each eye.

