6. STUDY INTERVENTION

6.1. Identity of Test Articles

The following contact lenses will be used in this study:

Table 1: Test Articles

	Test Lens
Name	Bausch + Lomb Ultra® Multifocal for Astigmatism
Manufacturer	Bausch + Lomb
Lens Material	Samfilcon A
Nominal Base Curve	8.6
Nominal Diameter	14.5
Nominal Distance Powers (D)	-1.00 to -4.00 in 0.25D steps, +1.00 to +4.00 in 0.25D steps
Nominal Cylinder Powers (D)	-0.75, -1.25
Cylinder axes (°)	70, 80, 90, 100, 110
Nominal ADD Power (D)	Low, High
Water Content	46%
Oxygen Permeability (Dk)	114.0
Wear Schedule in Current Study	Daily Reusable
Replacement Frequency	Monthly
Packaging Form (vial, blister, etc.)	Blister

Estimated number of lenses needed = 48 per SKU (90 axis) and 24 per SKU (other axes).

Clinical Study Protocol

Johnson & Johnson Vision Care, Inc.

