		Appendix E

Clinical Study Protocol
Johnson & Johnson Vision Care, Inc.

Visit 1: Baseline		
Step	Procedure	Details
		equivocal use the sighting dominance test to determine the dominant eye used for the study.
1.18	ADD Refinement	Place the BCC result in the trial frame and refine the near prescription with trial lenses (or flippers) under binocular conditions.
1.19	Near Visual Acuity	Using the ETDRS 2000 Series Chart 1 or 2 near card placed at 40 cm. Record the near visual acuity (OD, OS, OU).
1.20	Biomicroscopy	
FDA Slit Lamp Classification Scale will be used to grade the findings and determine eligibility.
 
If any of these slit lamp findings are Grade 2 or higher, the subject will be discontinued. If discontinued a final examination must be completed.
 
If the clearance of the fluorescein needs to be expedited, preservative-free rewetting drops may be instilled.

1.21	Eligibility after Baseline	
All responses to Inclusion Criteria questions must be answered “yes” and all responses to Exclusion Criteria questions must be answered “no” for the subject to be considered eligible.
 
If subject is deemed to be ineligible after baseline, proceed to Final Evaluation and complete all forms.

Visit 1: Treatment 1 Lens Fitting		
Step	Procedure	Details
1.22	Lens Selection	Select the lens power and axis based on the refraction and fitting guide for each eye. Record the test lens parameters (power and lot number).
1.23	Right Lens Insertion	Subjects will insert the right lens themselves. If the lens is uncomfortable, inspect for damage and remove, reinsert or replace as necessary.

Clinical Study Protocol
Johnson & Johnson Vision Care, Inc.

		Damaged lenses will be stored in labeled vial with Biotrue® multipurpose solution, and clearly differentiated from the other worn lenses that will be shipped back to the Sponsor. Complete the Quality Product Complaint form.	

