APPENDIX C: PACKAGE INSERT (APPROVED PRODUCT)

BAUSCH Health

DESCRIPTION: UltraMFA DW PIFG Ins / US / FITSET

PART No.: 8184600

SPEC No. or SPEC DIMENSIONS: 5573

SPECIAL INSTRUCTIONS: n/a

PRINT SUPPLIERS: Please refer to Bausch Health's *Print Supplier Guidelines*

BLACK

PMS
320

BAUSCH + LOMB

ULTRA® contact lenses

Multifocal for Astigmatism

with MoistureSeal® TECHNOLOGY

RX ONLY CAUTION: Federal law restricts this device to sale by or on the order of a licensed practitioner.

©TMare trademarks of Bausch & Lomb Incorporated or its affiliates.

© 2019 Bausch & Lomb Incorporated

Bausch & Lomb Incorporated

[name]

[name]

Printed in the USA

Rev. 2019-02
8184600

SYMBOL REFERENCE GUIDE

For labels and cartons:

	Meets EU Packaging Directive	BC	Base Curve
	Sterilized Using Steam	SVS	Single Vision Spherical
	Caution	ADD	Add Power
	Diameter	AX	Cylinder Axis
	Use-By Date	CYL	Cylinder Power
	Batch Code	SPH	Sphere Power
	Prescription Only (USA)	YYYY-MM-DD	Effective Date
	Power		Manufacturer

8 1 8 4 6 0 0

DESCRIPTION

The Bausch + Lomb ULTRA® (samfilcon A) Multifocal for Astigmatism Contact Lens material, samfilcon A, is a hydrophilic copolymer of a siloxane methacrylate and N-vinyl pyrrolidone, and is 46% water by weight when immersed in a sterile borate buffered saline with poloxamine solution. This lens is tinted with up to 200 ppm of Reactive Dye 246. The Bausch + Lomb ULTRA (samfilcon A) Multifocal for Astigmatism Contact Lenses utilizes MoistureSeal® Technology which creates a unique material and a hydrophilic surface.

The physical/optical properties of the lens are:

Specific Gravity:	1.048
Refractive Index:	1.411
Light Transmittance:	C.I.E. value—at least 95%
Water Content:	46%
Oxygen Permeability:	114 x 10 ⁻¹¹ [cm ³ O ₂ (STP) cm] / (sec x cm ² x mmHg) @ 35°C Polarographic Method (Boundary and Edge Corrected)

The Bausch + Lomb ULTRA (samfilcon A) Multifocal for Astigmatism Contact Lens features both a 3-Zone Progressive™ Design and an OpticAlign™ Design.

LENS PARAMETERS AVAILABLE

The Bausch + Lomb ULTRA (samfilcon A) Multifocal for Astigmatism Contact Lens is a hemispherical shell of the following dimensions:

Diameter:	14.5mm
Center Thickness:	0.05mm to 0.50mm
Base Curve:	8.6mm
Powers:	+4.00D to -6.00D in 0.25D steps
Add Powers:	Low (+0.75D to +1.50D) and High (+1.75D to +2.50D)
Cylinder Powers:	-0.75D, -1.25D and -1.75D
Axis:	10° to 180° in 10° increments

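### Eligibility admits cylinder up to -1.75 D but the study stocks the lens only in -0.75 and -1.25 D, so some eligible eyes keep more residual astigmatism than the marketed range would leave

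*Combined protocol and SAP*

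**What the plan says.** Inclusion criterion 8 (synopsis and section 3.2) requires that each subject "Have refractive cylinder in the range of -0.75 D to -1.75 D in each eye". Section 3.1 repeats the range: "Subjects to be enrolled will have -0.75 D to -1.75 D of astigmatism in both eyes".

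Table 1 in section 6.1 lists what sites will hold: "Nominal Cylinder Powers (D) -0.75, -1.25". The package insert in Appendix C lists three marketed cylinder powers, minus "0.75D, -1.25D and -1.75D".

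Section 1.2 acknowledges that "a limited range of refractive corrections (spheres, cylinders and axes) will be evaluated (see section 3.2"). That reference leads back to criterion 8 and so to -1.75 D.

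At Visit 1, step 1.22, the site is told to "Select the lens power and axis based on the refraction and fitting guide for each eye". Steps 1.33 and 2.11 to 2.22 allow lens changes, all from the same stock. Lenses are dispensed (steps 1.35 and 2.27) only if binocular distance acuity is 20/30 or better and the subject accepts the vision, comfort and fit.

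The first primary hypothesis (section 2.3) is that distance "logMAR visual acuity of the test lens will be statistically better than 0.00 logMAR". The intermediate and near thresholds are +0.17. Section 14.5 names age, gender and add power as possible covariates, but not cylinder. Section 14.9 rules out imputation.

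**The concern.** The eligible and supplied ranges disagree at the upper end of cylinder. For an eye at that end, the marketed power nearest the refraction is not at the site, and neither round of modification can supply it. The plan gives no reason for the omission and no analysis by cylinder.

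Sphere was handled differently. Criterion 7 asks subjects to "Have distance spherical component of refraction in the range of either -1.25 D to -3.75 D or +1.25 to +3.75 D in each eye", and Table 1 stocks 1.00 to 4.00 D in both signs, a margin of 0.25 D at each end. Cylinder stops 0.50 D short.

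The stated aim is to assess the acuity of a marketed lens. If a share of subjects wear less cylinder correction than that product can give, the primary estimates partly reflect the study's stock. Section 4.2 also plans to set the results beside studies of the sponsor's prototype.

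**Working it through.** The documents give no power, SD or bias figure to reproduce; section 14.2 says no power calculation was possible. The check is therefore of residual cylinder.

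**Inputs.** Eligible cylinder and sphere: section 3.2. Supplied powers: Table 1. Marketed powers: Appendix C. Vertex distance of 12 mm: assumed.

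**Spectacle plane.** Residual = refractive cylinder minus nearest lens cylinder, in absolute values.

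| Refractive cylinder (D) | Study stock | Marketed range |
|---|---|---|
| 0.75 | 0.00 | 0.00 |
| 1.00 | 0.25 | 0.25 |
| 1.25 | 0.00 | 0.00 |
| 1.50 | 0.25 | 0.25 |
| 1.75 | 0.50 | 0.00 |

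Only the last step differs.

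**Corneal plane.** Each meridian becomes F/(1 - 0.012F), and the cylinder is the difference between the two.

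- +3.75/-1.75: 3.75/0.955 = 3.927 and 2.00/0.976 = 2.049, so cylinder 1.878. Residual 0.628 with 1.25 D; 0.128 with 1.75 D.
- +1.25/-1.75: cylinder 1.766. Residual 0.516; 0.016.
- -1.25/-1.75: cylinder 1.664. Residual 0.414; 0.086 (over-corrected).
- -3.75/-1.75: cylinder 1.571. Residual 0.321; 0.179 (over-corrected).

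At -1.75 D the study stock therefore leaves 0.32 to 0.41 D in myopes and 0.52 to 0.63 D in hyperopes, against at most 0.18 D. The excess is 0.50 D in hyperopes (0.628 - 0.128) and 0.14 to 0.33 D in myopes (0.321 - 0.179; 0.414 - 0.086).

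At -1.50 D, hyperopes have a corneal cylinder of 1.518 to 1.614 D. The residual is 0.27 to 0.36 D with study stock and 0.14 to 0.23 D with the marketed range, so at the low end (0.268 against 0.232) the difference is trivial. Myopes at -1.50 D are unaffected.

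**Effect on the mean (illustration only).** Shift = share affected x excess residual x logMAR lost per dioptre. With assumed shares of 5 to 30%, an excess of 0.50 D and losses of 0.1 to 0.3 logMAR per dioptre, the range is 0.05 x 0.50 x 0.1 = 0.0025 to 0.30 x 0.50 x 0.3 = 0.045. The 0.50 D suits hyperopes and overstates myopes. The sum also treats the binocular endpoint as if both eyes were affected.

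For scale, the 95% half-width at n = 80 is 1.96 x SD/√80, or 0.018 to 0.026 for assumed SDs of 0.08 to 0.12. With assumed SD 0.10 (SE 0.0112) and true distance mean -0.03, the chance of meeting the distance criterion is Φ(0.03/0.0112 - 1.96), about 77%. A shift of 0.01 lowers it to about 43%.

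**The dispensing screen.** 20/30 is log10(1.5) = 0.176 logMAR, far looser than the 0.00 distance threshold, so many mildly under-corrected subjects could pass it.

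**Axis.** Eligible 65 to 115 degrees; supplied 70 to 110. An eye at 65 or 115 is 5 degrees from stock, and the marketed 10-degree steps give the same 5 degrees. The off-axis residual for a -1.25 D lens, 2 x 1.25 x sin(5°) = 0.22 D, is thus common to both ranges before any rotation.

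**The case against.** Several points limit the concern, and most of them stand.

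- **Scope.** Only eyes at -1.75 D and some hyperopic eyes at -1.50 D differ from the marketed range. A reader might infer that all 40 hyperopes are affected. The documents give no cylinder distribution, so the share is unknown.
- **Direction.** A reader might infer a certain bias in the mean. Subjects who find their vision unacceptable, or who miss 20/30, are not dispensed; section 8.2 withdraws subjects not successfully dispensed because of poor vision; and nothing is imputed. The worst-corrected may leave the analysis, offsetting part of the shift.
- **Mitigation.** Sphere can be adjusted after over-refraction. This may recover some acuity, but it cannot remove cylinder.
- **Fitting guide.** Its initial power-selection steps could not be read in the available text of Appendix C, so a rule for higher cylinders cannot be excluded. Such a rule still could not provide a power that is not stocked.
- **Prototype comparison.** A reader might infer that the marketed lens is put at a disadvantage. Section 4.2 describes the earlier studies as similar and does not give their cylinder limits. If those limits were the same, the comparison is like for like. It is in any case descriptive.
- **Axis.** The shorter supplied range matters only if lenses at the edge rotate outward, and the frequency of that is unknown.
- **Consequence.** Worse acuity makes the threshold tests harder to pass. Section 14.2 calls the study a pilot, and section 21 plans no publication.

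None of this reconciles criterion 8 with Table 1.

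**Conclusion.** The mismatch is real and follows from the documents' own figures. For -1.75 D eyes it leaves 0.32 to 0.63 D of residual cylinder, depending on sphere, against at most 0.18 D with the marketed range, assuming a 12 mm vertex distance. No permitted lens change removes it.

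The likely result is somewhat worse measured acuity and, for the threshold tests, a risk of false failure. The size in logMAR cannot be derived from the plan: the 0.0025 to 0.045 range rests wholly on assumed shares and losses. Some of the effect may show as non-dispensing or discontinuation. Bias in the prototype comparison is not shown. Severity is moderate: the plan needs reconciling and a sensitivity analysis, but the documents do not show that the primary results would be invalid without them.

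**What to change.** **Reconcile the text.** The sponsor should bring criterion 8 (synopsis and section 3.2), sections 1.2 and 3.1, and Table 1 into agreement on cylinder, and check the eligible against the supplied axes at the same time. Alternatively, state the limit openly and restrict the conclusion to the cylinder powers supplied. Which way to go is the sponsor's decision.

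**Add to the analysis in either case.**

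1. Before database lock, define a flag for subjects whose refractive cylinder exceeds what the supplied powers cover. One workable definition is a corneal-plane cylinder nearer to an unstocked marketed power than to any stocked one, with one-eye and two-eye cases distinguished.
2. Build it from the refraction at step 1.15 and the lens parameters at steps 1.22 and 2.13. Those steps name only power and lot number, so confirm that cylinder and axis are captured.
3. Report the distance, intermediate and near estimates with and without flagged subjects.
4. Tabulate non-dispensing and discontinuation for vision in the flagged group.

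**Cost.** One short amendment and one additional sensitivity table. Changing eligibility would affect recruitment. Changing supply would affect stock: each additional cylinder power means 26 spheres x 5 axes x 2 adds = 260 SKUs, or 52 x 48 + 208 x 24 = 7,488 lenses at Table 1's estimated quantities. Restricting the conclusion needs no change to either.
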